5 SYNOPSIS AND SCHEDULE OF EVENTS

5.1 Synopsis
Title of Study Protocol: A Phase 1b, Multiple Ascending-dose Study of EQ001 in Subjects with Systemic Lupus Erythematosus with or without Active Proliferative Lupus Nephritis
Protocol Number: EQ001-19-002
Name of Sponsor Company: Equillium, Inc.
Name of Finished Product: EQ001 (itolizumab)
Phase of Development: Phase 1b
Objectives:
Primary Objective
Characterize the safety and tolerability of EQ001 (itolizumab) in subjects with Systemic Lupus Erythematosus (SLE) with or without active proliferative Lupus Nephritis (apLN)
Secondary Objectives
1. Characterize the pharmacokinetic (PK) profile of EQ001
4. Characterize the clinical activity of EQ001 in Type B Cohort subjects Exploratory Objectives
2. Characterize the clinical activity of EQ001 in Type A Cohort subjects
Endpoints:
Primary Endpoints
Safety and tolerability of EQ001, as assessed by treatment-emergent adverse events (TEAEs), treatment-emergent serious adverse events (TESAEs), clinical laboratory values, vital signs, 12-lead electrocardiogram (ECG), and physical examinations.
Secondary Endpoints
1. Pharmacokinetics of EQ001, as assessed by EQ001 serum concentrations at specified timepoints.
4. Clinical activity of EQ001 in subjects with apLN, as assessed by the following variables):

Study Design:

This is a Phase 1b, multiple ascending-dose study to evaluate the safety, tolerability, PK, and clinical activity of EQ001, a humanized immunoglobulin G1 (IgG1) monoclonal antibody (mAb) that selectively targets CD6 on effector T cells (Teff), in subjects with SLE. Approximately 30 subjects with active or inactive SLE who do not have apLN are anticipated to be studied in dose escalation cohorts of 6 subjects each in Type A Cohorts. Up to approximately 20 subjects with apLN are anticipated to be studied in a Type B Cohort. Additional subjects may be added at the maximum-tolerated dose (MTD) cohort and/or to an additional cohort at an intermediate or lower dose in Type A. The exact numbers of each type of cohort will be determined by emerging data during the study.

To qualify for enrollment in the study, all subjects must have a diagnosis of SLE. Additionally, to qualify for enrollment in a Type B Cohort, subjects must have apLN, defined as proliferative LN (International Society of Nephrology [ISN]/Renal Pathology Society [RPS] Class III or IV with or without Class V) diagnosed by renal biopsy within 12 months prior to Day 1 or during Screening and previous evidence of serologic and clinical disease activity. Type B Cohort subjects may require induction treatment for apLN for newly diagnosed disease or relapsing/flaring disease or need additional treatment for incomplete response. Restricted SLE treatments (e.g., immunosuppressive medications and antimalarials) are required to be stable and/or washed out

Subjects in the Type B Cohort may have glucocorticoids administered and tapered.

Investigators will adhere to the protocol steroid taper schedule unless a safety concern (including concern related to insufficient response) necessitates departures from the schedule. Such planned departures must be discussed with the Medical Monitor, preferably in advance of the change in medication.

Type A

Type A will utilize a cohort dose escalation design. If < 2 of the 6 evaluable subjects in a Type A dose-escalation cohort experience a dose-limiting toxicity (DLT) during the DLT evaluation period (Days 1-29), then escalation may occur to the next higher dose level. If 2 or more of the 6 initial subjects in a Type A dose-escalation cohort experience a DLT, then no further dose escalation will occur. That dose will then be considered to have exceeded the MTD and the next-lower dose may be declared the MTD. Once a dose has been determined to have exceeded the MTD, the Data Review Committee (DRC) may recommend continuation of the study (with or without modification) and may expand enrollment to evaluate additional subjects at the MTD and/or in an additional cohort at an intermediate lower or dose to better define the MTD.

Type A Cohort enrollment will proceed in a sequential manner to evaluate escalating dose levels of EQ001. The first dose level to be studied, Dose Level 1, will be 0.4 mg/kg and the maximum dose level to be studied will be 3.2 mg/kg. Intermediate dose levels of 0.8, 1.6, and 2.4 mg/kg are planned for Type A Cohorts, but other intermediate doses may be chosen based on emerging PK, and safety data. Subjects in Type A Cohorts will receive a total of 2 doses, 2 weeks apart.

Equillium, Inc. Clinical Study Protocol No. EQ001-19-002 Page 12 of 110

The MTD determination will be made based only on Type A Cohorts. Dose escalation is allowed to proceed if no predefined stopping criteria are met and the DRC recommends that it is safe to proceed.

Type B

Up to approximately 20 subjects will be enrolled and dosed in the Type B Cohort. Subjects will receive a total of 13 doses of EQ001 1.6 mg/kg administered SC every 2 weeks over 24 weeks. All subjects must be on a stable dose of mycophenolate mofetil (MMF) or mycophenolic acid (MPA) for the duration of the study. Subjects that require induction treatment with pulse steroid treatment of methylprednisolone ≥500 mg or equivalent will undergo a rapid steroid taper with a 20% reduction per week. The targeted goal is to reach a prednisone dose of 10 mg or less per day by Week 10.

The study will be conducted in 3 defined periods, described below:

- 1. Screening Period
 - a. **Type A Cohorts:** The Screening Period for Cohort A subjects will be up to 4 weeks in duration, starting with the first screening procedure in the Schedule of Events (SOE; excluding the informed consent), and completed prior to Study Day 1 (Section 5.2)
 - b. **Type B Cohort:** The Screening Period for Cohort B subjects will be up to 6 weeks in duration (excluding the informed consent) and completed prior to Study Day 1 and may be completed over the course of multiple clinic visits. (Section 5.3).
- 2. Treatment Period
 - a. **Type A Cohorts**: The Treatment Period for Cohort A subjects will be 4 weeks in duration, beginning on Day 1 with the first study drug dose. During the Treatment Period, 2 doses of study drug will be

[figure not shown]
- administered subcutaneously (SC), 1 dose each on Days 1 and 15. Subjects will return to the study site for follow-up evaluations according to the SOE (Section 5.2).
- b. **Type B Cohort**: The Treatment Period for Cohort B subjects will be 24 weeks in duration, beginning on Day 1 with the first study drug dose. During the Treatment Period, 13 doses of study drug will be administered SC, 1 dose each on Days 1, 15, 29, 43, 57, 71, 85, 99, 113, 127, 141, 155, and 169. Subjects will return to the study site for follow-up evaluations according to the SOE (Section 5.3 and Section 5.4).
- 3. Follow-up Period
 - a. **Type A Cohorts**: The Follow-up Period for Cohort A subjects will end approximately 6 weeks after the last dose of study drug (Section 5.2)
 - b. **Type B Cohort**: The Follow-up Period for Cohort B subjects will end approximately 12 weeks after the last dose of study drug (Section 5.4)

Note: Contraception requirements must be continued for 130 days after the last dose of study drug for Type A and B Cohorts.

Written informed consent for study participation may be obtained up to 4 weeks prior to the Screening Visit for Type A Cohort subjects and 8 weeks prior to the Screening Visit for Type B Cohort subjects. Evaluation of eligibility will be based on laboratory results, medical history, concomitant and prior medications, vital signs, 12-lead ECG, physical examination, pregnancy testing (if applicable), and, in Type B Cohort, renal biopsy results.

Subjects will be evaluated for eligibility to receive the next dose based on laboratory and clinical criteria prior to each dose. The pre-dose laboratory evaluations may be performed at a local or central laboratory up to 14- days prior to the next target dosing day or on the target dosing day. If a subject discontinues study drug treatment prior to the last dose, they will be asked to return to the clinical study site to complete all follow up visits, as described in the SOE.

If a subject withdraws from the study, they should complete an Early Termination Visit.

added based on emerging data to meet the objectives of the study.

Inclusion Criteria:

Type A Cohort Inclusion Criteria. Subjects will be required to meet all of the following inclusion criteria in order to be eligible for study enrollment:

1. Is male or female, age \geq 18 and \leq 75 years

3. Has previously been documented to have met or currently meets Systemic Lupus International Collaborating Clinics (SLICC) and/or American College of Rheumatology (ACR) criteria for SLE

[figure not shown]
4. Received at least 1 immunosuppressive or immunomodulatory treatment (including antimalarials) for SLE at any time in the past or currently

6. Has documented elevation of antinuclear antibodies (ANA) in the past or during Screening

[figure not shown]
7. Restricted SLE treatments (e.g., other immunosuppressive medications, glucocorticoids, and antimalarials) are stable and/or washed out at Screening

[figure not shown]
8. Changes in SLE drug treatment(s), including increased doses of glucocorticoids or other SLE treatments, are not anticipated during the study

9. During Screening, has adequate hematologic function

Page 15 of 110

[figure not shown]

Equillium, Inc. Clinical Study Protocol No. EQ001-19-002 Page 17 of 110

Exclu	sion Criteria:
3.	A outs are abrenie infactions requiring systemic antibostopical antifungal or antivinal thereasy within 21 days
3.	Acute or chronic infections requiring systemic antibacterial, antifungal, or antiviral therapy within 21 days of Screening or active infection during Screening
4.	History of or Screening lab test positive for hepatitis B virus (HBV), hepatitis C virus (HCV), or human immunodeficiency virus (HIV)
6.	Active tuberculosis (TB) or a positive interferon-gamma release assay (IGRA) TB test

Equillium, Inc. Clinical Study Protocol No. EQ001-19-002 Page 19 of 110

Investigational Products, Dosage, and Mode of Administration:
The investigational product is EQ001 (itolizumab), a humanized recombinant IgG1 mAb that selectively targets the extracellular scavenger receptor cysteine-rich- (Sc) membrane-distal domain 1 of human CD6.
The planned doses and dosing regimen at each dose level The planned doses may be substituted for lower doses (including previously studied doses) based on accruing data. The highest dose level that will be studied is 3.2 mg/kg.
Measurements:
• Evaluation of safety will be performed by assessing adverse events, vital signs, 12-lead ECGs, physical examinations, and laboratory tests.
• Pharmacokinetics .
 Anti-drug antibodies (ADA) will be assessed, as well as neutralizing ADA in subjects that test positive for ADAs.
• Evaluation of clinical activity will be performed in all subjects using the SLEDAI-2K, patient-reported outcomes, serological markers, spot urine PCR, urinalysis, and serum complement. Clinical activity in apLN subjects will be evaluated with urine PCR (including 24-hour urine collections), eGFR, and doses of prednisone (or equivalent).
Statistical Methods:
All C - DV - 1 - C - 1 - C - T - A - 1

All safety, PK, and efficacy endpoints will be tabulated with descriptive statistics by cohort for Type A and for Type B portions of the study. Data may be pooled across cohorts.

Analysis Populations:

The study consists of the following analysis populations:

Safety Population: All subjects who receive any study drug.

PK Population: Subjects in the safety population who have at least one measurable post-EQ001 exposure serum concentration.

Clinical Study Protocol No. EQ001-19-002

Page 20 of 110

Efficacy Population: Subjects in the safety population who have at least 1 post-treatment assessment for a marker of clinical activity.

Safety Analyses:

Extent of exposure to the study treatment as measured by number of doses administered and duration of exposure to the study drug will be summarized using descriptive statistics. Adverse events (including DLTs) will be coded using the Medical Dictionary for Regulatory Activities (MedDRA) v 20.1, or higher version and graded using the National Cancer Institute (NCI) Common Terminology Criteria for Adverse Events (CTCAE v 5.0) for the purposes of data summarization. Incidence of TEAEs, TESAEs, TEAEs leading to study drug discontinuation,

TEAEs with an outcome of death will be summarized by MedDRA system organ class (SOC) and preferred term. Adverse events will also be summarized by worst CTCAE severity grade and causality relationship to study drug.

Clinical laboratory data will be descriptively summarized, including observed values at collection timepoints and change from baseline. All laboratory parameters that can be graded using CTCAE v 5.0 will be graded. For selected parameters, the following summaries may be produced:

- Worst post-baseline severity grade
- Shift summary of baseline grade to worst post-baseline severity grade

Safety evaluations may also include changes in the subject's vital signs, and ECG results. The incidence of treatment-emergent anti-EQ001 binding and neutralization antibodies will be reported.

PK Analyses:

Serum concentrations will be listed and summarized for each EQ001 dose using descriptive statistics for each cohort.

Efficacy Analyses:

apLN Subjects:

The geometric mean fold change from baseline in UPCR from a urine collection to FU1 and FU2 will be summarized descriptively, along with their 2-sided 95% CI for the fold change. The geometric mean fold change from baseline over time by visit will also be described.

The proportion of subjects with a > 30% and > 50% decline in UPCR and those with a UPCR < 500 mg/g at FU1 and FU2 will be described, along with their 2-sided 95% CI.

[figure not shown]
Time to UPCR decrease of > 50%, > 30%, and to a level of < 500 mg/g from baseline will be summarized using the Kaplan-Meier method. Baseline proteinuria is defined as the mean of the 2 UPCR measurements from 24-hour urine collections prior to Day 1 dosing. Descriptive analyses of serologic markers, eGFR, and prednisone use will be performed.

[figure not shown]
Subjects may be assessed based on the time since they had been on apLN treatment, such as MMF/MPA or time since pulse corticosteroids (i.e., >12 weeks vs < 12 weeks, or by quartiles). Additional subgroup analyses may be performed based on the data collection such as severity of lupus nephritis, baseline proteinuria or previous treatments.

Equillium, Inc. Clinical Study Protocol No. EQ001-19-002 Page 21 of 110

All Subjects: The changes in SLEDAI-2K scores from baseline will be summarized in both continuous and binary scale (e.g., decrease from baseline of ≥ 4 or < 4) with their 95% exact confidence intervals. Other measures of clinical activity of EQ001, such as change from baseline in autoantibody titers, serologic markers, and serum complement, will be summarized descriptively.

A detailed description of data analyses and statistical methods will be outlined separately in the Statistical Analysis Plan.

Equillium, Inc.	Clinical Study Protocol No. EQ001-19-002	Page 23 of 110

Equillium, Inc. Clinical Study Protocol No. EQ001-19-002 Pa	Page 29 of 110
---	----------------

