- Oral or similar contraceptive, which includes, but is not limited to: injectable, implanted, or patch hormone therapy, and hormone-containing intrauterine device (IUD);
- Non-hormonal IUD (must be used with another non-IUD method);
- Partner vasectomy at least 6 months prior to Screening.

For purposes of this study, females will be considered of childbearing potential unless they are naturally postmenopausal (i.e., no menses for 2 years) or permanently sterilized (i.e., bilateral tubal ligation, bilateral salpingectomy, bilateral oophorectomy, hysterectomy, or bilateral tubal occlusion with confirmation of occlusion by hysterosalpingogram).

Male subjects must have had a vasectomy at least 6 months prior to the first dose of the study drug or agree with their partner to use one of the acceptable birth control methods as listed above throughout the study and for 130 days after the last dose of study drug.

- 12. Is willing and able to comply with all protocol procedures and assessments required for the study
- 13. Is deemed by the investigator to be likely to comply with the protocol for the duration of the subject's participation in the study

9.1.2 Type B Cohort (Subjects with Active proliferative LN) Inclusion Criteria.

Subjects will be required to meet all of the following inclusion criteria in order to be eligible for study enrollment:

- 1. Is male or female, age \geq 18 and \leq 75 years
- 2. Has provided written informed consent prior to participation in the study in accordance with federal, local, and institutional guidelines
- 3. Has diagnosis of SLE
- 4. Kidney biopsy within 12 months prior to baseline or during Screening with a histologic diagnosis of LN (ISN/RPS 2003 classification of LN) Classes III, IV-S or IV-G, (A) or (A/C); Subjects with Class III or IV and concomitant Class V will be permitted.
- 5. Has a urine protein to creatinine ratio of > 1000 mg/g based on the mean of two 24-hour urine collections or a single urine protein to creatinine ratio of > 2000 mg/g based on a single 24-hour urine collection. The 2 collections must be within 12 weeks from Day 1 with 1 collected and resulted within 6 weeks of Day 1.

-		-
Ham	111111	n, Inc.
Lyun	ա	11, 1110.

Clinical Study Protocol No. EQ001-19-002

Page 53 of 110

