- 6. (All Regions except Asia-Pacific [APAC]) All subjects must be on MMF/MPA 2 to 3 g/day. For subjects that require induction treatment due to newly diagnosed LN or relapsing/flaring disease, subjects can have pulse systemic corticosteroids administered as part of their induction treatment.
 - (APAC) Requires induction treatment due to newly diagnosed LN or relapsing/flaring disease. Subjects need to be on MMF/MPA (2 to 3 g/day) and pulse systemic corticosteroids as part of their induction treatment. The MMF/MPA and pulse systemic corticosteroids can be started within 12 weeks prior to Day 1 or on Day 1.
- 7. Subjects that require induction treatment must receive at least 2 consecutive days of pulse systemic corticosteroids of methylprednisolone (≥500 mg) or equivalent and be able to receive it 12 weeks prior to Day 1 or start on Days 1 and 2; all induction subjects must be able to undergo a taper of systemic corticosteroids during the first 10 weeks of treatment.
- 8. Within 6 weeks of Day 1 has adequate hematologic function as defined by
 - a. ANC $> 1.5 \times 10^9/L$
 - b. ALC $\geq 1.0 \times 10^9/L$
 - c. Platelet count $> 75 \times 10^9/L$
 - d. Hemoglobin > 8.5 g/dL
- 9. Blood pressure ≤ 170/95 mm Hg without recent clinically significant changes per the investigator
- 10. The investigator considers the protocol-recommended steroid tapering schedule to be clinically appropriate for the subject based on the subject's current status and history
- 11. Has documented elevation of ANAs in the past or currently
- 12. The dose of MMF/MPA and other SLE drug treatments (other than glucocorticoids) are expected to remain stable during the study
- 13. Restricted SLE treatments (e.g., other immunosuppressive medications, antimalarials, ACE inhibitors, and angiotensin receptor blockers) are stable and/or washed out at Screening
- 14. Most recent eGFR ≥ 40 mL/min/1.73m² during Screening
- 15. No recent clinically significant changes in eGFR (increases or decreases) per the investigator
- 16. If the subject is a female of childbearing potential, she must be willing to practice complete abstinence, or she and any male partner are required to simultaneously use 2 effective contraceptive methods, from the following list of 5 methods below throughout the study and for 130 days after the last dose of study drug:
 - A barrier (condoms, diaphragm or cervical cap) with or without spermicide;
 - A second, different barrier method (condoms, diaphragm or cervical cap);

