Subjects who are pulsed and dosed with MMF/MPA during the Screening Period (within 12 weeks prior to starting study treatment) will be allowed into the study.

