6.1 General Methods

Statistical analysis of data from this study will be performed using SAS version 9.4 or higher.

Summaries of baseline characteristics (including demographics), safety, PD parameter receptor occupancy, and efficacy will be presented for each EQ001 dose level within each Type A cohorts and the Type B cohort as applicable. Additionally, data will also be summarized for all Type A subjects combined. A given dose may be studied in more than one cohort of Type A subjects and/or in Type B subjects. Selected safety summaries will also be produced that combine like doses across Type A and B cohorts.

Groups Presented for Baseline Characteristics, Safety, PD, and Efficacy Data Summaries

Type A Cohorts

- Dose 1
- Dose 2
- Dose 3
- Dose 4
- Dose 5
- All doses combined

Type B Cohort

Dose 1

Type A + Type B Cohort

Selected summaries that combine doses across Type A and B cohorts will be produced for the following: Adverse events by systemic organ class (SOC) and preferred terms, adverse events of special interest, serious adverse events, and adverse events resulting in study drug discontinuation. Like doses from Type A and Type B will be pooled, eg., Type A Dose 1.6 mg/kg combined with Type B Dose 1.6 mg/kg.

As the primary objective of this Phase 1b study is to characterize the safety and tolerability of EQ001, no formal statistical hypothesis testing will be performed. Confidence intervals (CIs) for selected clinical activity parameters may be presented for exploratory purposes only.

Most statistical summaries will be descriptive in nature. Unless otherwise indicated, continuous variables will be summarized using the number of observations (n), mean, standard deviation (SD), median, minimum, and maximum and categorical variables will be summarized using number of observations (n), frequency and percentages of subjects.

All dosed subjects will be included in subject data listings unless otherwise noted. If applicable, the relative day (i.e., relative to date of first dose of study treatment) of all complete dates will be presented in subject listings.

Data collected at unscheduled visits will also be included in the subject listings.

Adverse events, medical and surgical histories will be coded for summarization using the Medical Dictionary for Regulatory Activities (MedDRA[®] Version 23.1). Concomitant medications will be coded using the World Health Organization (WHO) Drug Dictionary Global B3 (March 2019 Version).

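### The Type B 24-hour UPCR baseline averages two pre-dose collections, so half of any fall between them counts as on-study decline, and no visible analysis varies that baseline

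*Protocol*

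**What the plan says.** **Baseline.** The Protocol 5.1 Synopsis, under efficacy analyses for apLN subjects, states: "Baseline proteinuria is defined as the mean of the 2 UPCR measurements from 24-hour urine collections prior to Day 1 dosing". SAP 8.1.1 uses a derived 24-hour UPCR baseline and refers to Section 6.2 for it. That section is not in the text available.

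**Timing of the collections.** Protocol 9.1.2, criterion 5, says: "The 2 collections must be within 12 weeks from Day 1 with 1 collected and resulted within 6 weeks of Day 1". It also offers a second way in: "or a single urine protein to creatinine ratio of > 2000 mg/g based on a single 24-hour urine collection".

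**Timing of induction.** For the Asia-Pacific region, criterion 6 says: "The MMF/MPA and pulse systemic corticosteroids can be started within 12 weeks prior to Day 1 or on Day 1". Criterion 7 requires induction subjects to receive pulse steroids and to "be able to receive it 12 weeks prior to Day 1 or start on Days 1 and 2"; Protocol 10.8.2.1 gives the same window. SAP 3.2 agrees: "Subjects who are pulsed and dosed with MMF/MPA during the Screening Period (within 12 weeks prior to starting study treatment) will be allowed". No visible text fixes the order of the two collections relative to the start of induction.

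**Use of the baseline.** SAP 8.1.1 divides each 24-hour UPCR value by the baseline. It summarizes the fold change, the proportions with >30% and >50% decline, and the times to those declines. Its sensitivity analysis drops late values and values after new LN treatment or a glucocorticoid increase. It leaves the baseline as it is.

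**The concern.** A mean of two values reduces measurement noise when the level is stable. Here the level may be moving. Induction may start between the collections, or it may have started before both with the response still under way at the second. In either case the mean overstates the level at which the subject enters treatment, and part of a fall that came before the first dose of EQ001 is reported as decline on EQ001.

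The Type B cohort has no control arm and up to about 20 subjects, so the fold change and the decline proportions will be read as the renal activity signal. At stake is how large that signal looks. The primary safety endpoint is unaffected, and the <500 mg/g endpoint does not use the baseline. The renal response definition (SAP Table 9) is not visible, so its dependence on the baseline cannot be checked.

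**Working it through.** The plan gives no figure for this effect, so there is nothing to reproduce first.

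**Inputs.** From the documents: baseline is the mean of two pre-dose values (read as arithmetic), fold change is visit value over baseline, the cut-offs are >30% and >50%, and the cohort is about 20. Assumed, because the documents do not give them: the fractional fall f between collections, and the number k of subjects with such a fall.

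**Step 1: baseline.** Let the first collection be U1 and the second U2 = U1(1 − f). The baseline is B = (U1 + U2)/2 = U1(1 − f/2). Then B − U2 = (U1 − U2)/2, which is half of the absolute fall.

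**Step 2: reported decline with no on-study change.** 1 − U2/B = f/(2 − f).

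**Step 3: on-study fall from U2 that must be exceeded to score above cut-off c.** 1 − (1 − c)(1 − f/2)/(1 − f).

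| f | Reported decline, no on-study change | Fall to exceed for >30% | Fall to exceed for >50% |
|---|---|---|---|
| 20% | 11.1% | 21.3% | 43.8% |
| 30% | 17.6% | 15.0% | 39.3% |
| 40% | 25.0% | 6.7% | 33.3% |
| 50% | 33.3% | none needed | 25.0% |
| 60% | 42.9% | none needed | 12.5% |

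**Step 4: pre-dose falls that score alone.** f/(2 − f) > 0.30 requires f > 0.60/1.30 = 46.2%. f/(2 − f) > 0.50 requires f > 1/1.5 = 66.7%.

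**Example.** Collections of 3000 and 1500 mg/g give a baseline of 2250. Staying at 1500 scores as a 33.3% decline. A later value of 1100 scores as 51.1%, although the fall from 1500 is 26.7%.

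**Opposite direction.** If the second value is 1.5 times the first (f = −0.5), no on-study change reads as −0.5/2.5 = −20%, that is, a 20% rise. Decline is then understated.

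**Step 5: cohort effect, illustration only.** With 20 subjects, no on-study change and k subjects sharing one f, the geometric mean fold change is [(1 − f)/(1 − f/2)]^(k/20). For k = 2 it is 0.98 (f = 30%) or 0.96 (f = 50%). For k = 5 it is 0.95 or 0.90.

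**Step 6: what a last-value baseline does.** For a fall between the collections with no later change, it reads 0% for every f. For a 50% fall after both collections but before Day 1 (3000, 3000, true Day 1 level 1500), both baselines read 50%.

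**Step 7: noise cost.** Let s be the error SD of one log value (equal, independent errors) and τ the between-subject SD of true log fold change. For collections at similar levels, the ratio of SDs of log fold change, last value against mean of two, is √[(τ² + 2s²)/(τ² + 1.5s²)]. This is 1.155 at τ = 0, 1.095 at τ = s and 1.044 at τ = 2s.

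**The case against.** The case against has several parts.

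- **The governing definition may be elsewhere.** SAP Section 6.2 may already settle timing and single collections. This stands: the point applies to the protocol definition and the visible analyses. A reader might infer that the SAP omits the matter, but the available text cannot show that.
- **Other planned outputs bear on it.** The Protocol 5.1 Synopsis foresees subgroups: "Subjects may be assessed based on the time since they had been on apLN treatment, such as MMF/MPA or time since pulse corticosteroids", with a 12-week cut or quartiles. SAP 8.1.1 analyses spot UPCR, whose baseline under the Protocol 13.1 default would be the last pre-dose value. SAP 7.6.3 summarizes time from last induction to first dose, and SAP 10.4 adds a listing of pre-induction laboratory findings. These give partial help. However, the subgroups are optional and spot urine is a different specimen. None of these outputs varies the 24-hour baseline.
- **Subjects with one collection are not necessarily without a baseline.** A reader might infer a gap, since they have no mean of two. The Protocol 13.1 default of the last non-missing pre-dose value is a natural fallback, so only confirmation is needed.
- **Averaging has a purpose.** It reduces noise and matches the two-collection eligibility measure. This is why it should stay as the main baseline.
- **The benefit is limited.** A last-value baseline leaves a fall after the last collection untouched, cannot separate EQ001 from continuing induction, and serves a descriptive endpoint for which "no formal statistical hypothesis testing will be performed" (SAP 6.1). All true. It still shows how much of the reported decline comes from averaging, which no visible output does.

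**Conclusion.** The concern holds as a conditional statement of modest weight. If 24-hour UPCR falls between the two pre-dose collections, the protocol's baseline counts half of the absolute fall as on-study decline: 18% for a 30% fall and 33% for a 50% fall, with no on-study change. If UPCR rises, decline is understated. The driver is change between the collections. An induction date lying between them is one cause; a continuing response to induction before both is another.

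A reader might go further and infer that the Type B decline will be largely an artefact of averaging, or that the mean of two is the wrong baseline. The documents support neither. They give no values for f or k, and the illustrated cohort effects run only from 0.98 to 0.90 under assumed inputs. Subjects with stable pre-dose UPCR, including those whose induction starts on Days 1 and 2, are not biased by averaging. The result rests on the protocol's definition being the one applied, which Section 6.2 must confirm.

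**What to change.** Keep the mean of two as the main baseline. Unless SAP Section 6.2 already provides for it, make these additions before the Type B database lock, if that has not yet occurred:

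- One prespecified sensitivity analysis of 24-hour UPCR fold change, >30% and >50% decline, and time to those declines, with the last pre-dose 24-hour value as baseline for all Type B subjects. This follows the Protocol 13.1 default.
- A listing of each Type B subject's ratio of second to first pre-dose collection, with both collection dates and the induction start date. Grouping subjects by whether induction falls between the collections would not be enough, because it would treat those still responding to earlier induction as unaffected.
- Confirmation of which baseline applies when only one collection exists: Section 6.2 or the Protocol 13.1 default.
- A statement that the sensitivity analysis does not remove a fall between the last collection and Day 1, or induction effects after Day 1.

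The cost is some SAP wording, a few descriptive outputs and a noisier baseline in the sensitivity analysis only: up to about 15% higher SD of log fold change, less if subjects truly differ in response. SAP 7.6.3 already uses the induction start date.
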